Appendix 1: Schedule of Activities (cont.)

Table 2: Chemotherapy Consolidation (cont.)

CTCAE=Common Terminology Criteria for Adverse Events; ECOG=Eastern Cooperative Oncology Group; eCRF=electronic Case Report Form; EDTA=ethylenediaminetetraacetic acid; EORTC=European Organisation for Research and Treatment of Cancer; EORTC QLQ-C30=EORTC Quality-of-Life Questionnaire–Core 30; EQ-5D-5L=EuroQol 5-Dimension, 5-Level; FACIT=Functional Assessment of Chronic Illness Therapy; HMRA=hematologic malignancy response assessment; MRD=minimal residual disease; PK=pharmacokinetic; PO=orally; PRO=patient-reported outcome; PRO-CTCAE=Patient-Reported Outcomes Common Terminology Criteria for Adverse Events; QD=once a day; QLQ-30=Quality-of-Life Questionnaire Core 30; RBR=Research Biosample Repository.

- ^a Vital signs include body temperature, systolic and diastolic blood pressure, pulse rate and respiratory rate. Body surface area will also be measured at screening.
- ^b Should D28 not be the last day of the cycle the following will be assessed every 7 days following D28 until end of treatment: biochemistry, hematology, vital signs, ECOG performance status. HMRA and whole blood sampling should be repeated last day of the cycle with D49 as limit if not done within the previous 2 weeks. Bone marrow sampling should not be repeated if already done within the last 56 days
- ^c All ECGs should be performed within 2 hours prior to idasanutlin administration and 6 hours after idasanutlin administration.
- ^d Includes systems of primary relevance (e.g., cardiovascular and respiratory systems), systems associated with symptoms (newly emergent or monitored from baseline), and areas associated with tumor assessment (lymph nodes, liver, spleen, and any other areas identified at baseline). Record new or worsened clinically significant abnormalities on the Adverse Event eCRF
- ^e All hematology and biochemistry assessments may be performed up to 3 days prior to the scheduled timepoint. Results must be reviewed by the investigator (or designee) PRIOR to study drug administration.
- ^f PRO questionnaires need to be self-administered before the patient receives any information on disease status and prior to the administration of study treatment. Completion of PROs should occur prior to the performance of non-PRO assessments whenever possible. PRO assessments include the FACIT-Fatigue, EORTC QLQ-C30, EORTC Item Library symptoms, PRO-CTCAE, and EQ-5D-5L.
- ^g For HMRAs during study, bone marrow aspirates are required, but bone marrow biopsies may be performed at the discretion of the investigator
- ^h Bone Marrow MRD/Flow, EDTA, and PAXgene to be collected at same time as bone marrow for response assessment. If unscheduled bone marrow aspirate is being collected for hematologic response assessment, then bone marrow MRD/Flow, EDTA, and PAXgene samples should also be collected. If any MRD assessments are done locally, please record this information in the eCRF. The priorities are MRD/Flow > EDTA > PAXgene.
- ⁱ EDTA only.
- ^j Refer to Section 4.3.2 for instructions on study treatment administration.

Appendix 1: Schedule of Activities (cont.)

Table 3: Maintenance in the Dose-Escalation Cohort and Expansion

| Assessment/Procedure | Maintenance (28-Day Cycle; ± 2 days) All Cycles | | | | | | |
|--|---|----|----|----|----|----------------|----------------|
| | D1 | D2 | D3 | D4 | D5 | D15 | D28 (Q3M) |
| Vital signs ^a , weight, ECOG performance status | x | | | | | | |
| Single 12-Lead ECG ^b | x | | | | | | |
| Targeted physical examination ^c | x | | | | | | |
| Urinalysis | x | | | | | | |
| FACIT-Fatigue, EORTC Item Library, EQ-5D-5L ^d | x ^e | | | | | | |
| PRO-CTCAE, EORTC QLQ-C30 ^d | x | | | | | | |
| Biochemistry ^f | x | | | | | x ^g | |
| Hematology ^f | x | | | | | x ^g | |
| HMRA | x | | | | | | x |
| Bone marrow sampling for HMRA ^h | x ⁱ | | | | | | x |
| RBR sampling Blood serum, plasma (optional) | x | | | | | | |
| Bone marrow sampling for MRD/Flow, EDTA, PAXgene [®] ^j | x ⁱ | | | | | | x |
| Whole blood sampling for EDTA and clinical | x | | | | | | x ^k |
| PK sampling | Refer to Appendix 2 | | | | | | |
| Concomitant medications | To be recorded continually; see Section 4.4 | | | | | | |
| Adverse events | To be assessed continually; see Section 5.3.1 | | | | | | |
| Idasanutlin (PO QD) ^l | x | x | x | x | x | | |

Appendix 1: Schedule of Activities (cont.)

Table 3: Maintenance in the Escalation Cohort and Expansion (cont.)

CTCAE=Common Terminology Criteria for Adverse Events; ECOG=Eastern Cooperative Oncology Group; eCRF=electronic Case Report Form; EDTA=ethylenediaminetetraacetic acid; EORTC=European Organisation for Research and Treatment of Cancer; EORTC QLQ-C30=EORTC Quality-of-Life Questionnaire–Core 30; EQ-5D-5L=EuroQol 5-Dimension, 5-Level; FACIT=Functional Assessment of Chronic Illness Therapy; HMRA=hematologic malignancy response assessment; MRD=minimal residual disease; PK=pharmacokinetic; PO=orally; PRO=patient-reported outcome; PRO-CTCAE=Patient-Reported Outcomes Common Terminology Criteria for Adverse Events; Q3M=once every 3 months; QD=once a day; RBR=Research Biosample Repository.

- ^a Vital signs include body temperature, systolic and diastolic blood pressure, pulse rate, and respiratory rate. Body surface area will also be measured at screening.
- ^b All ECGs should be performed within 2 hours prior to idasanutlin administration and 6 hours after idasanutlin administration.
- ^c Includes systems of primary relevance (e.g., cardiovascular and respiratory systems), systems associated with symptoms (newly emergent or monitored from baseline), and areas associated with tumor assessment (lymph nodes, liver, spleen, and any other areas identified at baseline). Record new or worsened clinically significant abnormalities on the Adverse Event eCRF.
- ^d PRO questionnaires need to be self-administered before the patient receives any information on disease status and prior to the administration of study treatment. Completion of PROs should occur prior to the performance of non-PRO assessments whenever possible. PRO assessments include the FACIT-Fatigue, EORTC QLQ-C30, EORTC Item Library symptoms, PRO-CTCAE, and EQ-5D-5L.
- ^e Every 3 months starting at Cycle 1.
- ^f All hematology and biochemistry assessments may be performed up to 3 days prior to the scheduled timepoint. Results must be reviewed by the investigator (or designee) PRIOR to study drug administration.
- ^g Only the first 3 cycles of maintenance.
- ^h For HMRAs during study, bone marrow aspirates are required, but bone marrow biopsies may be performed at the discretion of the investigator
- ⁱ Only required at maintenance Month 1 to confirm response in patients having received a transplant, bone marrow examination will require biopsy if an aspirate is not evaluable.
- ^j Bone marrow MRD/Flow, EDTA, and PAXgene to be collected at same time as bone marrow for response assessment. If unscheduled bone marrow aspirate is being collected for hematologic response assessment, then bone marrow MRD/Flow, EDTA, and Paxgene samples should also be collected. If any MRD assessments are done locally, please record this information in the eCRF. The priorities are MRD/Flow > EDTA > PAXgene.
- ^k EDTA only.
- ^l Refer to Section 4.3.2 for instructions on study treatment administration.

Appendix 1: Schedule of Activities (cont.)

Table 4: Maintenance in Post-Consolidation Cohort

| Assessment/Procedure | Screening ^a | Maintenance (28-Day Cycle; ± 2 days) All Cycles | | | | | | |
|--|------------------------|---|----|----|----|----|----------------|-----------|
| | Days – 14 to – 1 | D1 | D2 | D3 | D4 | D5 | D15 | D28 (Q3M) |
| Informed consent(s) ^b | x | | | | | | | |
| Demographics, medical history, determination of cytogenetic and molecular risk, physical examination, height, chest X-ray (or chest CT) ^c | x | | | | | | | |
| MUGA or ECHO | x | | | | | | | |
| Urinalysis | x | | | | | | | |
| Hepatitis B and C testing ^d | x | | | | | | | |
| C. difficile toxin and toxin-producing C. difficile in stool | x | | | | | | | |
| Serum pregnancy test ^e | x | | | | | | | |
| Coagulation (INR, aPTT [or PTT], and PT) | x | | | | | | | |
| Vital signs ^f , weight, ECOG performance status | x | x | | | | | | |
| Single 12-Lead ECG ^g | x | x | | | | | | |
| Targeted physical examination ^h | | x | | | | | | |
| Urinalysis | x | x | | | | | | |
| FACIT-Fatigue, EORTC Item Library, EQ-5D-5L ⁱ | | x ^j | | | | | | |
| PRO-CTCAE, EORTC QLQ-C30 ⁱ | | x | | | | | | |
| Biochemistry ^k | x | x | | | | | x ^l | |

Appendix 1: Schedule of Activities (cont.)

Table 4: Maintenance in Post-Consolidation Cohort (cont.)

| Assessment/Procedure | Screening ^a | Maintenance (28-Day Cycle; ± 2 day) All Cycles | | | | | | |
|---|------------------------|---|----|----|----|----|----------------|----------------|
| | Days – 14 to – 1 | D1 | D2 | D3 | D4 | D5 | D15 | D28 (Q3M) |
| Hematology ^k | x | x | | | | | x ^l | |
| HMRA | | | | | | | | x |
| Bone marrow sampling for HMRA ^m | x | | | | | | | x |
| Bone marrow sampling for MRD/Flow, EDTA, PAXgene ^{® n} | x | | | | | | | x |
| Whole blood sampling for flow, for EDTA and clinical | x | x | | | | | | x ^o |
| RBR sampling, blood serum and plasma (optional) | x | | | | | | | |
| PK sampling | | Refer to Appendix 2 | | | | | | |
| Concomitant medications | x | To be recorded continually; see Section 4.4 | | | | | | |
| Adverse events | | To be assessed continually; see Section 5.3.1 | | | | | | |
| Idasanutlin treatment (PO QD) ^p | | x | x | x | x | x | | |

AML=acute myeloid leukemia; CT=computed tomography; CTCAE=Common Terminology Criteria for Adverse Events; D=day; ECHO=echocardiogram; ECOG=Eastern Cooperative Oncology Group; eCRF=electronic Case Report Form; EDTA=ethylenediaminetetraacetic acid; EORTC=European Organisation for Research and Treatment of Cancer; EORTC QLQ-C30=EORTC Quality-of-Life Questionnaire–Core 30; EQ-5D-5L=EuroQol 5-Dimension, 5-Level; FACIT=Functional Assessment of Chronic Illness Therapy; HMRA=hematologic malignancy response assessment; MRD=minimal residual disease; MUGA= multiple-gated acquisition (scan); PK=pharmacokinetic; PO=orally; PRO=patient-reported outcome; PRO-CTCAE=Patient-Reported Outcomes Common Terminology Criteria for Adverse Events; Q3M=every 3 months; QD=once a day; RBR=Research Biosample Repository; TB=tuberculosis.

^a The screening period starts with the signing of the Informed Consent Form, including the optional Informed Consent Form if appropriate. Results of standard-of-care tests or examinations performed prior to obtaining informed consent and within the defined window may be used as screening and baseline assessments; such tests do not need to be repeated for screening purposes.

Appendix 1: Schedule of Activities (cont.)

Table 4: Maintenance in Post-Consolidation Cohort (cont.)

- ^b Informed consent must be documented before any study-specific screening procedure is performed.
- ^c If a chest CT is performed up to 28 days prior to study drug administration, a chest X-ray is not required. Patients with a medical history of fungal and TB infections should have a chest CT performed within 28 days prior to study drug administration. All data related to previous AML treatment such as but not limited to study drugs, regimens, doses, and dates will be collected.
- ^d Includes hepatitis B surface antigen, total hepatitis B core antibody, and hepatitis C virus antibody.
- ^e Must be performed within 7 days of the planned D1.
- ^f Vital signs include body temperature, systolic and diastolic blood pressure, pulse rate, and respiratory rate. Body surface area will also be measured at screening.
- ^g All ECGs should be performed within 2 hours prior to idasanutlin administration and 6 hours after idasanutlin administration.
- ^h Includes systems of primary relevance (e.g., cardiovascular and respiratory systems), systems associated with symptoms (newly emergent or monitored from baseline), and areas associated with tumor assessment (lymph nodes, liver, spleen, and any other areas identified at baseline). Record new or worsened clinically significant abnormalities on the Adverse Event eCRF.
- ⁱ PRO questionnaires need to be self-administered before the patient receives any information on disease status and prior to the administration of study treatment. Completion of PROs should occur prior to the performance of non-PRO assessments whenever possible. PRO assessments include the FACIT-Fatigue, EORTC QLQ-C30, EORTC Item Library symptoms, PRO-CTCAE, and EQ-5D-5L.
- ^j Every 3 months starting at Cycle 1.
- ^k All hematology and biochemistry assessments may be performed up to 3 days prior to the scheduled timepoint. Results must be reviewed by the investigator (or designee) PRIOR to study drug administration.
- ^l Only the first 3 cycles of maintenance.
- ^m At screening, bone marrow examination will require biopsy if an aspirate is not evaluable. For HMRA during the study, bone marrow aspirates are required, but bone marrow biopsies may be performed at the discretion of the investigator.
- ⁿ Bone marrow MRD/Flow, EDTA, and PAXgene to be collected at same time as bone marrow for response assessment. If unscheduled bone marrow aspirate is being collected for hematologic response assessment, then bone marrow MRD/Flow, EDTA, and PAXgene samples should also be collected. If any MRD assessments are done locally, please record this information in the eCRF. At screening, the priorities for bone marrow samples are EDTA > MRD Flow > PAXgene. At subsequent timepoints the priorities are MRD/FLOW > EDTA > PAXgene.
- ^o EDTA only.
- ^p Refer to Section 4.3.2 for instructions on study treatment administration.

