3.3.4.2 MRD Assessment

MRD responses are associated with improved outcomes, whereas patients who have MRD after induction and consolidation have a poor prognostic outcome (Jongen-Lavrencic et al. 2018).

MRD will be assessed as a secondary endpoint. Patients achieving remission will undergo additional serial MRD assessments at subsequent scheduled hematologic malignancy assessments ([Appendix 1](#)).

These MRD assessments will serve as an exploratory monitoring tool to investigate the depth of response and afford early detection of impending relapse (before cytomorphologic relapse occurs) after idasanutlin therapy.

In patients achieving remission, MRD monitoring from bone marrow aspirates will be prioritized over analysis of other exploratory markers.

MRD assessments can be made with the use of several technologies (e.g., by flow cytometry for abnormal cell phenotypes or leukemia-associated immune phenotype, by next-generation sequencing (NGS) of leukemia-associated mutations, or by polymerase chain reaction [PCR] technologies to detect AML-specific translocations or mutations). Recent reports suggest MRD in AML can also be assessed in cell-free DNA in plasma (Assi et al. 2018) and blood will be collected for this purpose.

MRD in this study will be primarily analyzed by flow cytometry. Other methods may be employed for orthogonal validation and exploration of the correlation of MRD detected in cell-free DNA with that in bone marrow aspirates.

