4.1.1.3 Inclusion Criteria for Patients in the Post-Consolidation Phase

Patients in the post-consolidation cohort must meet the following inclusion criterion for enrollment in the study:

- Documented/confirmed AML according to WHO (Arber et al. 2016) in remission after induction, within 21 days of end of last chemotherapy consolidation cycle, and were MRD positive at the end of induction as per local laboratory assessment (validated quantitative AML-specific MRD assessment with a >0.1% threshold)

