4.5.8.5 Bone Marrow

Bone marrow (i.e., aspirate and, if sampled, bone marrow biopsy for the analysis of biomarkers) will be collected at screening. Bone marrow aspirate will be collected each time that bone marrow is required for HMRA (see [Appendix 1](#)). If an unscheduled bone marrow aspirate is being collected to assess disease state, then additional bone marrow aspirate should be collected for flow and biomarker analyses. Procedures are described in detail in the laboratory manual(s).

- Bone marrow for MRD flow cytometry (heparin): Analysis will include determination of abnormal cell phenotypes by flow cytometry. After screening, the bone marrow for MRD flow cytometry is the priority sample.
- Bone marrow sample for DNA (in ethylenediaminetetraacetic acid [EDTA]): This is the priority bone marrow sample at screening. Mutation profiling, including TP53 and gene mutations, rearrangements, and fusions are commonly seen in patients with AML. The EDTA bone marrow will potentially be used for MRD monitoring by sequencing
- Bone marrow (PAXgene®): Analysis will include, but will not be limited to, gene expression analysis.

For patients who proceed to transplant, pre-transplant bone marrow samples for MRD and biomarkers should be obtained, when possible.

If sites do their own MRD assessments locally or collect mutational data, please provide this information in the eCRF.

If a patient consents to optional exploratory research, the remainder of the bone marrow sample(s) will be stored in the RBR (see Section 4.5.11) until they are no longer needed or until they are exhausted. However, the RBR storage period will be in accordance with the Institutional Review Board/Ethics Committee (IRB/EC)-approved Informed Consent Form and applicable laws (e.g., health authority requirements).

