6.3.3 Exploratory Efficacy Endpoints

All endpoints listed as primary and secondary will also be analyzed separately within the subset of patients with wild-type p53.

The following exploratory efficacy endpoints will also be assessed:

- MRD response over time (i.e., during induction, consolidation, and maintenance)
- Time to MRD-negative status, defined as time from initiation of treatment to confirmation of negative MRD status

Patients with continuing MRD positive status at the time of analysis will be censored at the date of last MRD assessment. Patients with no post baseline MRD assessment will be censored at Day 1.

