Appendix 1: Schedule of Activities (cont.)

Table 1: Induction (cont.)

- ⁿ Bone marrow MRD/Flow, EDTA, and PAXgene to be collected at same time as bone marrow for response assessment. If unscheduled bone marrow aspirate is being collected for hematologic response assessment, then bone marrow MRD/flow, EDTA, and PAXgene samples should also be collected. If any MRD assessments are done locally, please record this information in the eCRF. At screening, the priorities for bone marrow samples are EDTA>MRDFlow>PAXgene. At subsequent timepoints the priorities are MRD/Flow>EDTA>PAXgene.
- ^o EDTA only.
- ^p Refer to Section [4.3.2](#) for instructions on study treatment administration.

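### Post-consolidation screening marrow ranks DNA above MRD flow although patients enter in remission, so a scant aspirate can forfeit the only pre-dose flow MRD; p53 status from remission marrow needs its own rule

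*Combined protocol and SAP*

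**What the plan says.** **Tube order.** Table 4, footnote n (maintenance in the post-consolidation cohort): "At screening, the priorities for bone marrow samples are EDTA > MRD Flow > PAXgene". From the next timepoint on, the same footnote puts MRD flow first. Table 1, footnote n, gives newly diagnosed patients the identical screening order: "At screening, the priorities for bone marrow samples are EDTA>MRDFlow>PAXgene". Section 4.5.8.5 says of the EDTA DNA sample: "This is the priority bone marrow sample at screening". Of flow it says: "After screening, the bone marrow for MRD flow cytometry is the priority sample". It does not distinguish cohorts.

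**MRD principle.** Section 3.3.4.2: "In patients achieving remission, MRD monitoring from bone marrow aspirates will be prioritized over analysis of other exploratory markers", and "MRD in this study will be primarily analyzed by flow cytometry".

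**Cohort and endpoint.** Section 4.1.1.3 requires patients to be "in remission after induction, within 21 days of end of last chemotherapy consolidation cycle, and were MRD positive at the end of induction", the MRD result coming from the local laboratory. Section 6.1 plans 30 patients. Section 6.3.2 analyses the share who turn from MRD-positive to MRD-negative on treatment, with the same exact 90% interval as the primary endpoint. It does not say which MRD measurement is the baseline.

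**p53.** Section 6.3.3: "All endpoints listed as primary and secondary will also be analyzed separately within the subset of patients with wild-type p53". Section 4.5.8.5 uses the EDTA marrow for mutation profiling including TP53. Section 4.5.1 requires cytogenetics from diagnosis as a minimum and calls molecular markers desirable.

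**The concern.** DNA-first suits an untreated marrow full of leukemic cells. The post-consolidation cohort is the opposite case: little leukemia is left, and the question is whether the residue clears on idasanutlin. When marrow is short, the stated order protects the DNA tube and puts the pre-dose flow result at risk.

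That result matters because the qualifying MRD test was done at the end of induction, before consolidation. If it serves as baseline, a patient whom consolidation had already cleared counts as converting on idasanutlin. With a single arm, no comparison separates the two effects.

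A second, independent issue is that DNA from a remission marrow may contain too few leukemic cells to show a TP53 mutation. A mutant leukemia could then enter the wild-type subset.

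**Working it through.** **1. The orders side by side**

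| Place | Patients' state | Order |
|---|---|---|
| Table 1, fn n, screening | untreated AML | EDTA, MRD flow, PAXgene |
| Table 4, fn n, screening | in remission | EDTA, MRD flow, PAXgene |
| Section 4.5.8.5, screening | not separated | EDTA first |
| Table 2, fn h (consolidation) | in remission | MRD flow, EDTA, PAXgene |
| Table 3, fn j (maintenance) | in remission | MRD flow, EDTA, PAXgene |
| Table 4, fn n, later visits | in remission | MRD flow, EDTA, PAXgene |
| Table 5, fn d (post-treatment) | follow-up | MRD flow, EDTA, PAXgene |
| Section 3.3.4.2 | achieving remission | MRD before other exploratory markers |

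Post-consolidation screening is the one remission-stage timepoint where flow is not first. No reason is given.

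**2. Is there another pre-dose marrow?** No. Table 4 schedules marrow at screening and then on Day 28 every 3 months.

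**3. How often is the flow tube lost?** The documents give no rate. Flow is second of three, so an aspirate that cannot fill every tube loses PAXgene first. If 10% to 20% of aspirates cannot fill all three (assumption), flow is lost in at most 30 × 0.10 = 3 to 30 × 0.20 = 6 patients. The actual number may be much smaller.

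**4. Effect on the conversion endpoint**

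*If the end-of-induction result stands in.* Spurious conversions = 30 × l × q, where l is the share of flow tubes lost and q the share already MRD-negative at screening. Both are assumed. Already-negative patients are taken to stay negative on at least one later test.

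| l | q = 10% | q = 30% | q = 50% |
|---|---|---|---|
| 10% | 0.3 | 0.9 | 1.5 |
| 20% | 0.6 | 1.8 | 3.0 |

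At l = 20% this is 2, 6 or 10 percentage points on 30. If the end-of-induction result were the baseline for everyone (l = 100%), the figures would be 3, 9 and 15. The unnamed baseline can therefore matter more than tube order.

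*If patients without a flow baseline are dropped.* Method check: exact 90% Clopper-Pearson limits give 49.2–86.0% for 14/20 and 65.6–95.8% for 17/20, matching Tables 14 and 15. With an illustrative conversion rate near 30%:

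| Lost | Converted/n | 90% CI (%) | Width (points, from unrounded limits) |
|---|---|---|---|
| 0% | 9/30 | 16.6–46.5 | 29.9 |
| 10% | 8/27 | 15.7–47.1 | 31.5 |
| 20% | 7/24 | 14.6–47.9 | 33.3 |
| 30% | 6/21 | 13.2–48.7 | 35.5 |

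The loss of precision is modest. The possible bias is the larger worry.

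**5. TP53 in remission marrow.** Appendix 19 requires under 5% marrow blasts for CR. For a heterozygous mutation carried by all leukemic cells, with normal copy number, allele fraction = leukemic fraction / 2: 5% gives 2.5%, 1% gives 0.5%, and 0.1% (the entry MRD threshold) gives 0.05%. With an assumed call rule of at least 5 mutant reads, the binomial chance of detection is:

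| Allele fraction | 500 reads | 1000 reads |
|---|---|---|
| 2.5% | 99.5% | about 100% |
| 0.5% | 10.8% | 56.0% |
| 0.05% | about 0% | about 0% |

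Depth and call rule are assumptions, since the documents state neither.

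**The case against.** **The plan follows its own rule.** Section 4.5.8.5 ranks EDTA first at screening, and footnote n agrees. Section 3.3.4.2 can be read as covering only later, on-study monitoring. A reader might infer that footnote n breaches the plan's stated priority. The documents do not support that: there is a tension between Section 3.3.4.2 and Section 4.5.8.5, and neither section considers a cohort that enters in remission.

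**The loss is rare and partly covered.** Section 4.5.6 asks sites to allow for flow and sequencing when drawing marrow. The EDTA tube may serve MRD by sequencing, local MRD results go into the eCRF, and the end-of-induction result is required for entry. Table 4 also draws blood for flow at screening, though the stated use of pretreatment blood flow is MDM2 expression (Section 3.3.4.1). This stands as mitigation. It does not supply a pre-dose marrow result by the study's main method, and sequencing is only a possibility.

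**The p53 point is separate.** It comes from sampling in remission, and reordering tubes would not cure it. The subset is exploratory, and CR at the end of induction does not apply to a cohort induced before entry. Nothing says p53 status here must come from remission marrow. All of this stands, but no rule says where the status should come from.

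**Conclusion.** The point holds as a gap in cohort-specific wording. The screening order is not adapted to a cohort in remission, and the baseline for its conversion endpoint is not named. A very scant aspirate can cost the only pre-dose marrow flow MRD, for an unquantified few of 30 patients.

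Two stronger readings are not supported. The first is that 3 to 6 patients will lack a baseline: that is a ceiling under an assumed 10% to 20% shortfall, because flow is the second tube. The second is that the wild-type p53 subset is contaminated: a mutation can be missed, but this depends on an unstated assay limit, and the number of TP53-mutant patients in the cohort is unknown. Near the 5% blast limit, detection would be good under the assumptions used. Around 1% leukemic cells it becomes unreliable, and near 0.1% it fails.

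The spurious-conversion figures rest on assumed loss and clearance rates and on substituting the end-of-induction result.

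**What to change.** 1. In Table 4, footnote n, and in Section 4.5.8.5, set the screening order for the post-consolidation cohort to MRD/Flow > EDTA > PAXgene. Leave Table 1 as it is.
2. In Section 6.3.2, name the screening marrow flow result as the baseline for conversion. State how a missing baseline is handled and how patients already negative at screening are counted.
3. In Section 6.3.3, take this cohort's p53 status from the diagnostic-sample result where available. Class a negative result from remission marrow alone as unknown, not wild-type.

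**Cost.** Wording in the protocol and laboratory manual; no new sample or visit. A few patients may lack remission-marrow DNA, although EDTA whole blood is also drawn at screening. Some will have unknown p53 status, so the wild-type subset shrinks. Patients already negative at screening cannot convert: if 30% were, 30 × 0.70 = 21 would remain, with the 35.5-point width shown for 6/21.
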